7.2.2 Reporting of Pregnancy and Lactation to the Sponsor

Although pregnancy and lactation are not considered adverse events, it is the responsibility of investigators or their designees to report any pregnancy or lactation in a subject (spontaneously reported to them) that occurs during the trial or within 120 days of completing the trial (Last dose of study drug for MK-3475 treated patients, or last blood draw for non-treated controls) or 30 days following cessation of treatment if the subject initiates new anticancer therapy, whichever is earlier. All subjects who become pregnant must be followed to the completion/termination of the pregnancy. Pregnancy outcomes of spontaneous abortion, missed abortion, benign hydatidiform mole, blighted ovum, fetal death, intrauterine death, miscarriage and stillbirth must be reported as serious events (Important Medical Events). If the pregnancy continues to term, the outcome (health of infant) must also be reported.

Such events must be reported within 24 hours to the Sponsor either by electronic media or paper. Sponsor Contact information can be found in the Investigator Trial File Binder (or equivalent).

7.2.3 Immediate Reporting of Adverse Events to the Sponsor

7.2.3.1 Serious Adverse Events

A serious adverse event is any adverse event occurring at any dose or during any use of Sponsor's product that:

- Results in death;
- Is life threatening;
- Results in persistent or significant disability/incapacity;
- Results in or prolongs an existing inpatient hospitalization;
- Is a congenital anomaly/birth defect;
- Is a new cancer (that is not a condition of the study);
- Is associated with an overdose;
- Is an other important medical event

Refer to [Table 11](#) for additional details regarding each of the above criteria.

Progression of the cancer under study is not considered an adverse event unless it results in hospitalization or death.

Any serious adverse event, or follow up to a serious adverse event, including death due to any cause that occurs to any subject from the time the consent is signed through 90 days following cessation of treatment (for MK-3475 treated patients), or 14 days following the last blood draw (for non-treated controls), or 30 days following cessation of treatment if the subject initiates new anticancer therapy, whichever is earlier, whether or not related to the Sponsor's product, must be reported within 24 hours to the Sponsor either by electronic media or paper. Sponsor Contact information can be found in the Investigator Trial File Binder (or equivalent).

Additionally, any serious adverse event, considered by an investigator who is a qualified physician to be related to the Sponsor's product that is brought to the attention of the investigator at any time outside of the time period specified in the previous paragraph also must be reported immediately to the Sponsor.

All subjects with serious adverse events must be followed up for outcome.

7.2.3.2 Events of Clinical Interest

Selected non-serious and serious adverse events are also known as Events of Clinical Interest (ECI) and must be recorded as such on the Adverse Event case report forms/worksheets and reported within 24 hours to the Sponsor either by electronic media or paper. Sponsor Contact information can be found in the Investigator Trial File Binder (or equivalent).

Events of clinical interest for this trial include:

1. an overdose of Sponsor's product, as defined in Section 7.2.1 - Definition of an Overdose for This Protocol and Reporting of Overdose to the Sponsor, that is not associated with clinical symptoms or abnormal laboratory results.
2. an elevated AST or ALT lab value that is greater than or equal to 3X the upper limit of normal and an elevated total bilirubin lab value that is greater than or equal to 2X the upper limit of normal and, at the same time, an alkaline phosphatase lab value that is less than 2X the upper limit of normal, as determined by way of protocol-specified laboratory testing or unscheduled laboratory testing.*

***Note:** These criteria are based upon available regulatory guidance documents. The purpose of the criteria is to specify a threshold of abnormal hepatic tests that may require an additional evaluation for an underlying etiology. The trial site guidance for assessment and follow up of these criteria can be found in the Investigator Trial File Binder (or equivalent).

7.2.3.3 Surgical complications

All subjects enrolled in this clinical trial will undergo SOC surgical RCC tumor resection. Control subjects will proceed to surgery without study-related treatment, while patients randomized to receive neoadjuvant MK-3475 will proceed to surgery 2-3 weeks following the final MK-3475 dose. As such, any surgical complications in the intra- and postoperative period (30 days from the time of surgery) will be recorded, and will include but will not be limited to the following:

1. the need for and the volume of blood transfusions in the perioperative period
2. hospital readmission following discharge
3. thromboembolic events
4. cardiovascular events
5. pulmonary complications
6. gastrointestinal complications
7. postoperative infection
8. incision-related complications

7.2.4 Evaluating Adverse Events

An investigator who is a qualified physician will evaluate all adverse events according to the NCI Common Terminology for Adverse Events (CTCAE), version 4.0. Any adverse event which changes CTCAE grade over the course of a given episode will have each change of grade recorded on the adverse event case report forms/worksheets.

All adverse events regardless of CTCAE grade must also be evaluated for seriousness.

Table 11 Evaluating Adverse Events

An investigator who is a qualified physician, will evaluate all adverse events as to:

| | | |
|----------------------------------|---|--|
| V4.0 CTCAE Grading | Grade 1 | Mild; asymptomatic or mild symptoms; clinical or diagnostic observations only; intervention not indicated. |
| | Grade 2 | Moderate; minimal, local or noninvasive intervention indicated; limiting age-appropriate instrumental ADL. |
| | Grade 3 | Severe or medically significant but not immediately life-threatening; hospitalization or prolongation of hospitalization indicated; disabling; limiting self-care ADL. |
| | Grade 4 | Life threatening consequences; urgent intervention indicated. |
| | Grade 5 | Death related to AE |
| Seriousness | A serious adverse event is any adverse event occurring at any dose or during any use of Sponsor's product that: | |
| | † Results in death ; or | |
| | † Is life threatening ; or places the subject, in the view of the investigator, at immediate risk of death from the event as it occurred (Note: This does not include an adverse event that, had it occurred in a more severe form, might have caused death.); or | |
| | † Results in a persistent or significant disability/incapacity (substantial disruption of one's ability to conduct normal life functions); or | |
| | † Results in or prolongs an existing inpatient hospitalization (hospitalization is defined as an inpatient admission, regardless of length of stay, even if the hospitalization is a precautionary measure for continued observation. (Note: Hospitalization for an elective procedure to treat a pre-existing condition that has not worsened is not a serious adverse event. A pre-existing condition is a clinical condition that is diagnosed prior to the use of a Merck product and is documented in the patient's medical history.); or | |
| | † Is a congenital anomaly/birth defect (in offspring of subject taking the product regardless of time to diagnosis); or | |
| | Is a new cancer ; (that is not a condition of the study) or | |
| | Is an overdose (whether accidental or intentional). Any adverse event associated with an overdose is considered a serious adverse event. An overdose that is not associated with an adverse event is considered a non-serious event of clinical interest and must be reported within 24 hours. | |
| | Other important medical events that may not result in death, not be life threatening, or not require hospitalization may be considered a serious adverse event when, based upon appropriate medical judgment, the event may jeopardize the subject and may require medical or surgical intervention to prevent one of the outcomes listed previously (designated above by a †). | |
| Duration | Record the start and stop dates of the adverse event. If less than 1 day, indicate the appropriate length of time and units | |
| Action taken | Did the adverse event cause the Sponsor's product to be discontinued? | |
| Relationship to test drug | Did the Sponsor's product cause the adverse event? The determination of the likelihood that the Sponsor's product caused the adverse event will be provided by an investigator who is a qualified physician. The investigator's signed/dated initials on the source document or worksheet that supports the causality noted on the AE form, ensures that a medically qualified assessment of causality was done. This initialed document must be retained for the required regulatory time frame. The criteria below are intended as reference guidelines to assist the investigator in assessing the likelihood of a relationship between the test drug and the adverse event based upon the available information. The following components are to be used to assess the relationship between the Sponsor's product and the AE ; the greater the correlation with the components and their respective elements (in number and/or intensity), the more likely the Sponsor's product caused the adverse event (AE): | |
| | Exposure | Is there evidence that the subject was actually exposed to the Sponsor's product such as: reliable history, acceptable compliance assessment (pill count, diary, etc.), expected pharmacologic effect, or measurement of drug/metabolite in bodily specimen? |
| | Time Course | Did the AE follow in a reasonable temporal sequence from administration of the Sponsor's product? Is the time of onset of the AE compatible with a drug-induced effect (applies to trials with investigational medicinal product)? |
| | Likely Cause | Is the AE not reasonably explained by another etiology such as underlying disease, other drug(s)/vaccine(s), or other host or environmental factors |

| Relationship to Sponsor's Product (continued) | The following components are to be used to assess the relationship between the test drug and the AE: (continued) | |
|--|--|---|
| | Dechallenge | Was the Sponsor's product discontinued or dose/exposure/frequency reduced? If yes, did the AE resolve or improve? If yes, this is a positive dechallenge. If no, this is a negative dechallenge. (Note: This criterion is not applicable if: (1) the AE resulted in death or permanent disability; (2) the AE resolved/improved despite continuation of the Sponsor's product; or (3) the trial is a single-dose drug trial); or (4) Sponsor's product(s) is/are only used one time.) |
| | Rechallenge | Was the subject re-exposed to the Sponsor's product in this study? If yes, did the AE recur or worsen? If yes, this is a positive rechallenge. If no, this is a negative rechallenge. (Note: This criterion is not applicable if: (1) the initial AE resulted in death or permanent disability, or (2) the trial is a single-dose drug trial); or (3) Sponsor's product(s) is/are used only one time). NOTE: IF A RECHALLENGE IS PLANNED FOR AN ADVERSE EVENT WHICH WAS SERIOUS AND WHICH MAY HAVE BEEN CAUSED BY THE SPONSOR'S PRODUCT, OR IF REEXPOSURE TO THE SPONSOR'S PRODUCT POSES ADDITIONAL POTENTIAL SIGNIFICANT RISK TO THE SUBJECT, THEN THE RECHALLENGE MUST BE APPROVED IN ADVANCE BY THE SPONSOR CLINICAL DIRECTOR AS PER DOSE MODIFICATION GUIDELINES IN THE PROTOCOL. |
| | | The assessment of relationship will be reported on the case report forms /worksheets by an investigator who is a qualified physician according to his/her best clinical judgment, including consideration of the above elements. |
| Record one of the following | | Use the following scale of criteria as guidance (not all criteria must be present to be indicative of a Sponsor's product relationship). |
| Yes, there is a reasonable possibility of Sponsor's product relationship. | There is evidence of exposure to the Sponsor's product. The temporal sequence of the AE onset relative to the administration of the Sponsor's product is reasonable. The AE is more likely explained by the Sponsor's product than by another cause. | |
| No, there is not a reasonable possibility of Sponsor's product relationship | Subject did not receive the Sponsor's product OR temporal sequence of the AE onset relative to administration of the Sponsor's product is not reasonable OR there is another obvious cause of the AE. (Also entered for a subject with overdose without an associated AE.) | |

7.2.5 Sponsor Responsibility for Reporting Adverse Events

All Adverse Events will be reported to regulatory authorities, IRB/IECs and investigators in accordance with all applicable global laws and regulations.

8.0 STATISTICAL ANALYSIS PLAN

8.1 Statistical Analysis Plan Summary

This section contains a brief summary of the statistical analyses for this trial. Full detail is in the Statistical Analysis Plan (SAP) (Section 8.2).

Primary Safety

Incidence of adverse experiences will be descriptively summarized for all adverse experiences and Grade 3 or 4 adverse experiences separately. Summary statistics and plots will be generated for the change from baseline values in the vital signs, ECG parameters, and selected laboratory safety parameters for subjects, as deemed clinically appropriate. Depending on the safety parameter, the difference from baseline will either be computed on the original scale (raw change from baseline) or on the log scale and back- transformed for reporting (percent change from baseline). Summary statistics for the raw laboratory safety tests, ECGs, and/or vital signs may also be computed, as deemed clinically appropriate.

Primary PD Hypothesis

To assess the primary PD hypothesis, the posterior probability that the true response rate is at least 30% will be calculated based on a beta-binomial Bayesian model. A beta prior with parameters $\alpha=0.1$ and $\beta=0.1$ will be assumed. The primary PD hypothesis will be met with at least 80% posterior probability at interim analysis 1, at least 70% posterior probability at interim analysis 2, or at least 60% posterior probability at interim analysis 3.

Interim Analysis: There will be up to 3 interim analyses done for this study. Details of the interim analysis strategy are provided in Section 8.2.6.

Power

Safety

If no AE of a given type is observed in any subject receiving neoadjuvant MK-3475, then the true incidence of the adverse experience at that dose is at most 13%, 10%, 9%, 6%, or 5% with 80% confidence when the sample size among those receiving neoadjuvant MK-3475 is 12, 15, 18, 24 or 33, respectively.

Pharmacodynamics

If the true immune infiltration response rate is 40%, there is ~85% power to meet the primary hypothesis at either the second or third interim analysis, or at the end of the study. If the true response rate is 45%, there is ~85% to meet the primary hypothesis at either the second or third interim analysis. To have high power (>80%) to meet the primary hypothesis after the second interim analysis, the true response rate must be greater than or equal to 55%.

8.2 Statistical Analysis Plan

The statistical analysis of the data obtained from this study will be conducted by, or under the direct auspices of, the Early Clinical Development Statistics Department in collaboration with the Discovery Medicine Department of the Sponsor.

If, after the study has begun, changes are made to the statistical analysis plan stated below, then these deviations to the plan will be listed, along with an explanation as to why they occurred, in the Results Memo for this study.

8.2.1 Hypotheses

Primary (Safety)

[figure not shown]
Neoadjuvant MK-3475 treatment will be well tolerated in patients undergoing subsequent surgical RCC tumor resection.

Primary (PD)

Neoadjuvant MK-3475 therapy will stimulate a 2-fold or greater increase in intratumoral lymphocytic infiltration in at least 30% of patients with RCC.

[figure not shown]
Secondary (PD)

1. 

Tertiary (PD)

8.2.2 Analysis Endpoints

Primary Safety

The primary safety endpoints in this study include all types of adverse experiences, in addition to laboratory safety assessments, ECGs, and vital signs.

[figure not shown]
Primary PD

The primary PD endpoint in this study is the intratumoral lymphocytic infiltration in patients with RCC. Patients with at least a 2-fold increase in intratumoral lymphocytes will be considered immune cell infiltration responders.

Secondary PD

[figure not shown]

Tertiary PD

Exploratory PD

There are several exploratory endpoints in this study that include the following:

8.2.3 Approaches to Analyses

The following populations are defined for the analysis and reporting of data. All subjects will be reported, and their data analyzed, according to the treatment(s) they actually received.

All Subjects as Treated (AST) - All subjects who received at least one dose of the investigational drug. This population will be used for assessments of safety and tolerability.

Per-Protocol (PP) – The set of data generated by the subset of subjects who comply with the protocol sufficiently to ensure that these data will be likely to exhibit the effects of treatment, according to the underlying scientific model. Compliance covers such considerations as exposure to treatment, availability of measurements and absence of major protocol violations. Major protocol violators will be identified to the extent possible by individuals responsible for data collection/compliance, and its analysis and interpretation. Any subjects or data values excluded from analysis will be identified, along with their reason for exclusion, in the Results Memo for this study. At the end of the study, all subjects who are compliant with the study procedure as aforementioned and have available data

from at least one treatment will be included in the primary analysis dataset. This population will be used for the all PD analyses.

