3.0 OBJECTIVE(S) & HYPOTHESIS(ES)

3.1 Primary Objective(s) & Hypothesis(es)

[figure not shown]
(1) **Objective:** To assess the safety of neoadjuvant MK-3475 therapy in patients undergoing surgical resection for the treatment of RCC

Hypothesis: Neoadjuvant MK-3475 treatment will be well tolerated in patients undergoing subsequent surgical RCC tumor resection.

[figure not shown]
(2) **Objective:** To assess the effect of neoadjuvant MK-3475 therapy on immune cell infiltration in RCC

Hypothesis: Neoadjuvant MK-3475 therapy will stimulate a 2-fold or greater increase in intratumoral lymphocytic infiltration in at least 30% of patients with RCC.

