4.2.3 Rationale for Endpoints

4.2.3.1 Safety Endpoints

The primary safety objective of this trial is to characterize the safety and tolerability of MK-3475 administered in a neoadjuvant setting in patients with RCC. The primary safety analysis will be based on subjects who experienced toxicities as defined by CTCAE criteria. Safety will be assessed by quantifying the toxicities and grades, including serious adverse events (SAEs) and events of clinical interest (ECIs), experienced by all subjects who have received MK-3475.

Safety will be assessed by reported adverse experiences using CTCAE, Version 4.0. The attribution to drug, time-of-onset, duration of the event, its resolution, and any concomitant medications administered will be recorded. AEs to be analyzed will include but will not be limited to all AEs, SAEs, fatal AEs, and laboratory changes. Furthermore, potential immune-related adverse events (irAEs) will be collected and designated as immune-related events of clinical interest (ECIs) as described in Section 7.2.3.2.

Because all patients with RCC treated with neoadjuvant MK-3475 in this trial will undergo subsequent SOC operative tumor resection, surgical complications will be assessed. The following information related to surgery will be recorded: blood transfusions in the perioperative period, length of hospital stay, readmission, and surgical complications including the need for surgical re-exploration, thromboembolic events, cardiovascular events, pulmonary complications, gastrointestinal complications, postoperative infection, and incision-related complications.

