5.2 Trial Treatment(s)

The treatment to be used in this trial is outlined below in [Table 2](#).

Table 2 Trial Treatment

| Biologic | Dose/ Potency | Dose Frequency | Route of Administration | Regimen | Use |
|----------|------------------|-------------------|----------------------------|--------------------------|---------------------------------|
| MK-3475 | 200 mg | Q3 weeks | IV | 2 (or up to 3*) doses | Experimental, Neoadjuvant |
| MK-3475 | 200 mg | Q3 weeks | IV | Up to 17 doses† | Experimental, Post-Resection |

*Potential increase in number of doses will be based on interim analysis (see Section 8.0).
†MK-3475 doses may be withheld due to toxicity, as described in Section 5.2.1.2.

Trial Treatment should begin within 28 days of randomization or treatment assignment for those randomized to receive neoadjuvant MK-3475.

The investigator shall take responsibility for and shall take all steps to maintain appropriate records and ensure appropriate supply, storage, handling, distribution and usage of trial treatments in accordance with the protocol and any applicable laws and regulations.

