For randomized subjects only, AEs that occur from the time the consent is signed through the time of randomization will only be reported as AEs if they are the result of a protocol-specified intervention, including but not limited to washout or discontinuation of usual therapy, diet, placebo treatment or a procedure. All AEs will be recorded from the time of randomization through 30 days following cessation of treatment (for MK-3475 treated patients), or 14 days following the last blood draw (for non-treated controls), and at each examination, on the AE case report forms/worksheets. The reporting timeframe for adverse events meeting any serious criteria is described in section 7.2.3.1. The investigator will make every attempt to follow all subjects with non-serious adverse events for outcome.

Electronic reporting procedures can be found in the Electronic Data Capture (EDC) data entry guidelines. Paper reporting procedures can be found in the Investigator Trial File Binder (or equivalent).

Progression of the cancer under study is not considered an adverse event unless it results in hospitalization or death.

7.2.1 Definition of an Overdose for This Protocol and Reporting of Overdose to the Sponsor

For purposes of this trial, an overdose of pembrolizumab will be defined as any dose of 1,000 mg or greater (≥ 5 x the indicated dose). No specific information is available on the treatment of overdose of pembrolizumab. In the event of overdose, the subject should be observed closely for signs of toxicity. Appropriate supportive treatment should be provided if clinically indicated.

If an adverse event(s) is associated with (“results from”) the overdose of Sponsor's product or vaccine, the adverse event(s) is reported as a serious adverse event, even if no other seriousness criteria are met.

If a dose of Sponsor's product or vaccine meeting the protocol definition of overdose is taken without any associated clinical symptoms or abnormal laboratory results, the overdose is reported as a non-serious Event of Clinical Interest (ECI), using the terminology “accidental or intentional overdose without adverse effect.”

All reports of overdose with and without an adverse event must be reported within 24 hours to the Sponsor either by electronic media or paper. Sponsor Contact information can be found in the Investigator Trial File Binder (or equivalent).

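### The primary adverse event summary is not tied to the neoadjuvant phase: the only safety set is anyone ever dosed, and no rule separates neoadjuvant from post-resection events

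*Combined protocol and SAP*

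**What the plan says.** **The question.** Section 3.1 gives the first primary objective as "To assess the safety of neoadjuvant MK-3475 therapy in patients undergoing surgical resection for the treatment of RCC". Section 8.2.1 gives the hypothesis as "Neoadjuvant MK-3475 treatment will be well tolerated in patients undergoing subsequent surgical RCC tumor resection". Section 4.2.3.1 states the aim as to "characterize the safety and tolerability of MK-3475 administered in a neoadjuvant setting in patients with RCC".

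**The set.** Section 8.2.3 defines one safety population, the as-treated set (AST), in these words: "All subjects who received at least one dose of the investigational drug. This population will be used for assessments of safety and tolerability". It adds: "All subjects will be reported, and their data analyzed, according to the treatment(s) they actually received". Section 4.2.3.1 counts toxicities "experienced by all subjects who have received MK-3475", without naming a phase.

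**The summary.** Section 8.2.4 describes AE incidence overall and for Grade 3 or 4 events. It gives no period, phase or denominator.

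**The period.** Section 7.2 says: "All AEs will be recorded from the time of randomization through 30 days following cessation of treatment (for MK-3475 treated patients". The end of treatment is not tied to a phase. Sections 5.2.1.1 and 7.1.5.6 let all subjects have up to 17 doses after surgery.

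**What is already phase-specific.** Surgical complications are limited to 30 days from surgery (section 7.2.3.3) and summarised for neoadjuvant recipients (section 8.2.4). Table 13 and the zero-event statement in section 8.2.7 use neoadjuvant recipients as the denominator.

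**The concern.** The primary safety question is how well patients tolerate two or three doses before and around surgery. The AST is defined by ever having been dosed, so it answers a different question: what happened over the whole trial to anyone who received the drug. Two things enter that do not belong to the primary question:

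- events during up to a year of post-resection dosing in neoadjuvant recipients;
- controls whose first dose came after resection.

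The protocol's own argument for the hypothesis depends on length of exposure. Section 4.2.1.5 cites Grade 3-5 AE incidences in melanoma of about 11% and 18% at exposures matching two and three doses, against about 47% after 300 or more days. It expects clearly fewer events during the short course. A whole-trial incidence cannot test that expectation. No threshold is set for good tolerability, so the AE table is itself the evidence, and its population and window should be fixed before an open-label trial is tabulated.

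**Working it through.** **1. Reproduce the plan's precision figures (section 8.2.7).** The chance of at least one event is 1 − (1 − p)^n. At p = 10% and n = 24 it is 1 − 0.9^24 = 92.0% (stated 92). All 15 cells of Table 13 reproduce after rounding. The one-sided 80% upper bound with no events is 1 − 0.2^(1/n):

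| n | 12 | 15 | 18 | 24 | 33 |
|---|---|---|---|---|---|
| computed % | 12.55 | 10.17 | 8.55 | 6.49 | 4.76 |
| stated % | 13 | 10 | 9 | 6 | 5 |

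The figures are right for neoadjuvant recipients. The AST can reach 36, where the bound is 1 − 0.2^(1/36) = 4.4% and the Table 13 column would read 30, 84 and 98. The safety set and the precision statements therefore describe different groups.

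**2. Share of the AST that never had neoadjuvant drug, if all controls are later dosed** (arm sizes from Table 4 and section 8.2.6).

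- Control randomization continues: 6/18 = 9/27 = 12/36 = 33%.
- Control randomization stops: 3/18 = 17%, 3/27 = 11%, 3/36 = 8%.

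**3. Share of a neoadjuvant recipient's maximum planned doses given after resection.** 17/(2 + 17) = 89%; 17/(3 + 17) = 85%. This is a share of doses, not of AEs, and applies only to subjects who complete optional post-resection dosing.

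**4. Illustration of the gap.** Use the section 4.2.1.5 rates: 11% for the two-dose phase and 47% for anyone who goes on to post-resection dosing, controls included. Uptake u is not stated in the documents, so it is varied and assumed unrelated to earlier events. At 24 neoadjuvant and 12 control subjects:

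- AST size = 24 + 12u
- subjects with an event = 24[0.11(1 − u) + 0.47u] + 12u × 0.47

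| u | AST size | with event | AST rate | neoadjuvant-phase rate |
|---|---|---|---|---|
| 0 | 24 | 2.6 | 11% | 11% |
| 0.5 | 30 | 9.8 | 33% | 11% |
| 1 | 36 | 16.9 | 47% | 11% |

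At 33 and 3 the AST rates are 11%, 30% and 47%. The independence assumption is not strictly true: under section 5.2.1.2.1.1, non-metastatic subjects with drug-related toxicity above Grade 1 in the neoadjuvant phase do not go on.

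**5. Direction of the difference.** Let p1 be the neoadjuvant-phase risk, pW the whole-trial risk in neoadjuvant recipients and pC the control risk. Within neoadjuvant recipients, pW cannot be below p1. Pooled at 24/12:

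(24pW + 12pC)/36 > p1 ⇔ pW − p1 > 0.5(p1 − pC).

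At 33/3 the factor is 3/33 = 0.09.

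**6. Is there an obvious default cut-off?** Section 7.1.5.4 puts surgery about 14 to 21 days after the last neoadjuvant dose. Flow chart 6.4 starts post-resection dosing at 45 ± 15 days after surgery.

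- A hypothetical analysis cut 30 days after the last neoadjuvant dose falls 30 − 21 = 9 to 30 − 14 = 16 days after surgery, inside the 30-day complication period.
- A 90-day cut overlaps post-resection dosing, which starts 14 + 30 = 44 to 21 + 60 = 81 days after that dose.

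Neither fits on the planned schedule, so the rule has to be written down.

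**The case against.** **The intent is visible.** Section 8.2.7 names neoadjuvant recipients as the denominator, and section 4.2.3.1 opens with the neoadjuvant setting. The as-treated sentence, "All subjects will be reported, and their data analyzed, according to the treatment(s) they actually received", read with Table 2, which lists "Experimental, Neoadjuvant" and post-resection as separate uses, may allow separate columns. This largely stands as evidence of intent, and nothing says that the phases will be pooled. But most neoadjuvant recipients may receive both treatments, and the sentence gives no rule for placing an event in such a subject.

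**The effect is limited.** Primary safety is descriptive, surgical complications already have a window and a group, and the dates needed for phase tables are collected. All of this stands. Flow chart 6.4 also lists no vital signs or ECGs and leaves most laboratory tests to the physician, so the gap falls mainly on AEs.

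**Stronger readings that the documents do not support.**

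- A reader might infer from "All AEs will be recorded from the time of randomization through 30 days following cessation of treatment (for MK-3475 treated patients" that collection stops soon after surgery in a neoadjuvant subject with no later dose. The same sentence also requires recording at each examination, and section 7.1.5.5 has all subjects assessed for AEs 30 to 42 days after resection.
- A reader might infer that controls' period before post-resection dosing is shorter by a fixed number of days. Section 7.1.5.4 allows control surgery up to 6 weeks after randomization, so any such figure is only nominal.
- A reader might see the omission of never-dosed controls from the AST as a defect. The objective concerns treated patients, and section 8.2.4 says that controls are too few for accurate comparison.

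**Conclusion.** The point holds for AEs. Followed literally, sections 8.2.3 and 8.2.4 give a whole-trial AE incidence in anyone ever dosed. That does not estimate neoadjuvant tolerability and does not match the denominators in section 8.2.7. Up to a third of the set (12 of 36), or 3 of 36 if control randomization stops, could be subjects without neoadjuvant drug.

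The size of the distortion in the AE rate cannot be fixed from the documents. It depends on post-resection uptake and on control risk. The 11% against 33% or 47% contrast is an illustration from melanoma rates under assumed uptake, not a prediction. A reader might infer that a pooled table must overstate neoadjuvant risk, but step 5 shows that this holds only when the later increment in neoadjuvant recipients outweighs any lower control risk.

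No formal test, error rate or decision rule is affected. The harm is to what the AE table can be taken to mean for one of the two primary objectives. This is a cheap improvement worth making.

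**What to change.** In sections 8.2.3 and 8.2.4:

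1. Base the primary AE summary on all subjects with at least one neoadjuvant dose. Count AEs that start or worsen from that first dose to just before the first post-resection dose. If there is none, count to the later of the post-operative visit and the end of protocol AE collection. List events between randomization and first dose, including biopsy events, separately, since no drug had yet been given.
2. Report post-resection AEs separately, by randomized arm, among subjects with at least one post-resection dose.
3. Keep the overall AST table as supportive, so that late immune-related AEs are not lost.
4. State that the section 8.2.7 precision figures apply to the set in (1).
5. Limit any descriptive display against controls to the shared period from surgery to the post-operative visit.

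The cost is SAP wording and one extra set of AE tables. No new data or visits are needed: section 7.2.4 already records start and stop dates and each change of grade, and flow chart 6.4 puts the post-operative visit before post-resection dosing. The limitation is that neoadjuvant toxicity appearing after post-resection dosing begins cannot be attributed to a phase. Section 5.2.1.2 notes that immune-related events can arise months after the last dose, which is the reason for item 3.
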